## 5 STATISTICAL METHODS

All descriptive statistics for continuous variables will be reported using mean, standard deviation (SD), median, Q1, Q3, minimum and maximum, otherwise will be specified. Categorical variables will be summarized as number (percent) of subjects. All summarized variables will also be listed for each subject. Statistical analyses will be performed using SAS software or other validated statistical software as required.

### 5.1 Study Endpoints

#### 5.1.1 Primary Endpoint

The primary endpoint is PFS assessed by IIR, defined as the time from the date of randomization to the date of the first documentation of disease progression or death (whichever occurs first) using RECIST 1.1 ([Eisenhauer et al., 2009](#)). PFS censoring rules will follow the FDA guidance of 2007 ([FDA, 2007](#)) and will be detailed in subsequent section.

#### 5.1.2 Secondary Endpoints

- Objective response rate (ORR), defined as the proportion of subjects who have best overall response (BOR) of CR or PR as determined by IIR using RECIST 1.1. ORR will be calculated for confirmed CR/PR, and for confirmed and unconfirmed CR/PR. Confirmed CR/PR will be primary for ORR analysis.
- Overall survival (OS), defined as the time from the date of randomization to the date of death from any cause. Subjects who are lost to follow-up and those who are alive at the date of data cutoff will be censored at the last date the subject was last known alive, or date of data cutoff, whichever occurs first.
- Safety will be assessed summarizing the incidence of treatment-emergent adverse events (TEAEs) and SAEs together with all other safety parameters.
- Proportion of subjects who discontinue treatment due to toxicity is defined as the proportion of subjects who discontinue study treatment due to treatment-emergent adverse events (TEAEs).
- Time to treatment failure is defined as time from the date of randomization to the date that a subject discontinues study treatment due to TEAEs.
- Health-Related Quality of Life (HRQoL), assessed using the Functional Assessment of Cancer Therapy Kidney Syndrome Index-Disease-Related Symptoms (FKSI-DRS), the European Organization for the Research and Treatment of Cancer (EORTC) QLQ-C30 and the European Quality of Life (EuroQOL) EQ-5D-3L instruments. This analysis will be detailed in a separate SAP for HRQoL.
- PFS on next-line therapy (PFS2), defined as the time from randomization to disease progression on next-line treatment or death from any cause (whichever occurs first).
- Progression-free survival (PFS) by investigator assessment is defined as the time from the date of randomization to the date of first documentation of disease

progression based on the investigator assessment per RECIST v.1.1 or death (whichever occurs first).

- Pembrolizumab PK comparison to historical data. This analysis will be detailed in a separate SAP for PK/PD.
- Model-predicted clearance and AUC for lenvatinib in Arms A and B. This analysis will be detailed in a separate SAP for PK/PD.
- Model-predicted clearance and AUC for everolimus in Arm A. This analysis will be detailed in a separate SAP for PK/PD.

### 5.1.3 Exploratory Endpoints

Exploratory efficacy endpoints will be:

- Objective response rate (ORR), defined as the proportion of subjects who have best overall response (BOR) of CR or PR as determined by investigator assessment using RECIST 1.1.
- Duration of response (DOR) is defined as the time from the date a response of CR or PR by IIR and investigator assessment was first documented until the date of the first documentation of disease progression or date of death from any cause.
- Disease control rate is the proportion of subjects who have best overall response of CR or PR or SD by IIR and investigator assessment. Stable disease must be achieved at  $\geq 7$  weeks after randomization to be considered best overall response.
- Clinical benefit rate is the proportion of subjects who have best overall response of CR or PR or durable SD (duration of SD  $\geq 23$  weeks after randomization) by IIR and investigator assessment.
- Blood and tumor biomarkers will be assessed for identifying potential correlation with clinical outcomes-related endpoints. This analysis will be detailed in a separate SAP for biomarkers.

For exploratory efficacy endpoints that involve with CR/PR, the endpoint will be calculated once for confirmed CR/PR, and once for confirmed and unconfirmed CR/PR.

## 5.2 Study Subjects

### 5.2.1 Definitions of Analysis Sets

The following analysis sets will be defined:

- The Full Analysis Set (Intent-to-Treat Analysis [ITT] Population) is the group of all randomized subjects regardless of the treatment actually received. This is the primary analysis population used for all efficacy analyses which will be based on the intent-to-treat principle.
- The Per Protocol Analysis Set is the subjects who received at least one dose of

any study drug, had no major protocol deviations and had both baseline and at least 1 postbaseline tumor assessments. Subjects who died prior to the first postbaseline tumor assessment will also be included. The per protocol analysis set will be the secondary analysis set for efficacy endpoints.

- The Safety Analysis Set is the group of subjects who received at least one dose of any study drug. This is the analysis population for all safety analyses, which will be based on as-treated principle.
- Population Pharmacokinetic (PK) Analysis Set: All subjects who have received at least one dose of study treatment with documented dosing history in the lenvatinib plus everolimus arm (Arm A) or the lenvatinib plus pembrolizumab arm (Arm B), and have measurable plasma levels of lenvatinib or whole blood levels of everolimus.

**Table 1 Analysis Sets in Data Analysis**

Data Category	Full	Per Protocol	Safety
Protocol Deviations	•		
Disposition	•		
Demography & Baseline Characteristics	•		
Disease History	•		
Prior & Concomitant Medications	•		
Progression-Free Survival	•	•	
Tumor Response	•	•	
Overall Survival	•	•	
Drug Exposure			•
Adverse Events			•
Deaths			•
Laboratory Tests			•
Vital Signs			•
ECGs			•
Echocardiography			•

- Pembrolizumab PK Analysis Set: All subjects who have received at least one dose of study treatment with documented dosing history in the lenvatinib plus pembrolizumab arm (Arm B) and have measurable serum concentrations of pembrolizumab.

- The Pharmacodynamic Analysis Set is the group of subjects who received at least one dose of study drug and had sufficient pharmacodynamic data to derive at least one pharmacodynamic parameter and with documented dosing history.
- The HRQoL Analysis Set will consist of all subjects who have any HRQoL data.

Table 1 shows each analysis set to be primarily used in each data category but not limited to the specifications in this table.

### 5.2.2 Subject Disposition

Enrolled subjects include all subjects who signed informed consent forms. The number of subjects screened and the number (percent) of subjects who failed screening and the reasons for screen failure will be summarized, based on data reported on the Screening Disposition Case Report Form (CRF).

The number of subjects randomized, treated, prematurely discontinued from study drug, and those with major protocol deviations will be counted by site and by treatment arms. The number of subjects who discontinued one medication but remained on other medication in Arm A and Arm B will also be summarized. The primary reason for study drug discontinuation will be summarized by treatment arms and overall according to the categories in the corresponding CRFs.

The end of study status: alive (still on treatment or on follow up), death, withdrew consent, lost to follow-up or study terminated by sponsor at the data cutoff date will also be summarized by treatment arms and overall.

### 5.2.3 Protocol Deviations

Major protocol deviation criteria will be established and subjects with major protocol deviations will be identified and documented before the database lock for the primary analysis. Major protocol deviations will be appropriately summarized by center and grouped into different categories. All major protocol deviations identified according to study entry criteria and during treatment will be listed, broken down by center.

### 5.2.4 Demographic and Other Baseline Characteristics

Demographic and baseline characteristics for the Full Analysis Set will be summarized for each treatment arm and overall using descriptive statistics for the following variables. They include but are not limited to age, sex, race, race group, ethnicity, weight, height, body mass index (BMI), geographic region, Karnofsky performance status (KPS), KPS score group, MSKCC prognostic group, International Metastatic Renal Cell Carcinoma Database Consortium (IMDC) prognostic group and PD-L1 status. Disease history and characteristics at study entry, previous anticancer medications and previous radiotherapies will be summarized. Palliative radiotherapy on treatment for RCC will be listed separately.

Subject listings of medical history and non-pharmacological procedures on treatment will be provided.

### 5.2.5 Prior and Concomitant Therapy

All investigator terms for medications recorded in the CRF will be coded to an 11-digit code using the World Health Organization Drug Dictionary (WHO DD) version of March 2018 or later. The number (percentage) of subjects who took prior and concomitant antihypertensive, antidiarrheal medications and corticosteroids for systemic use will be summarized on the Full Analysis Set by treatment arm, Anatomical Therapeutic Chemical (ATC) class 1, pharmacological class 3, and WHO DD preferred term. Other prior and concomitant medications, excluding antihypertensive, antidiarrheal medications and corticosteroids for systemic use will be summarized similarly. If a subject has taken prior and concomitant medications more than once within the same preferred term, the subject will be counted only once for the respective preferred term. Prior medications are defined as medications that started prior to the first dose of study drug. Concomitant medications are defined as medications that (1) started before the first dose of study drug and were continuing at the time of the first dose of study drug, or (2) started on or after the date of the first dose of study drug up to 30 days after the subject's last dose. A medication that cannot be determined as prior/concomitant/post treatment due to missing/incomplete dates will be regarded as a concomitant medication. All medications will be presented in subject data listings.

## 5.3 Data Analysis General Considerations

Tumor response will be assessed by IIR and the investigator based on RECIST 1.1 for all three arms. Analyses will be performed separately for assessments by IIR and by the investigator, but the primary endpoint is progression-free survival as assessed by IIR.

All stratified efficacy analyses will be based on strata recorded in the IxRS system at randomization as primary. The concordance and discordance of strata between IxRS and the clinical database will be summarized in frequency and percentage by treatment arms and listed by treatment arm and subject.

### 5.3.1 Pooling of Centers

This study is a multicenter, international study. Subjects from all centers for each region will be pooled and region will be used as one of the two stratification factors for most of efficacy analyses.

[figure not shown]
### 5.3.2 Adjustments for Covariates

Cox proportional hazards models and log-rank tests for PFS and OS, and the Cochran-Mantel-Haenszel (CMH) test of ORR will be stratified by region (West Europe and North America, Rest of World), and MSKCC Risk Group (favorable, intermediate, and poor risk). Analyses of the primary endpoint PFS will also include other covariates of interest by means of subgroups.

### 5.3.3 Multiple Comparisons/Multiplicity

To adjust for multiplicity and provide strong control of the overall family-wise error rate (FWER), the graphical approach of Maurer and Bretz (Maurer et al., 2013) will be used in the primary endpoint of PFS and the key secondary efficacy endpoints (OS and ORR). No multiplicity adjustment will be made for other secondary endpoints analyses and exploratory endpoints analyses. Subgroup analyses in Section 5.3.4 will be considered as exploratory analyses and no multiplicity adjustment will be made.

An  $\alpha$  of 0.0001 will be subtracted from the total  $\alpha$  of 0.05 to account for the interim analysis of ORR from Arm B. Figure 2 shows the initial  $\alpha$ -allocation (the remaining  $\alpha = 0.0499$ ) for each hypothesis and the graphical approach for multiple analyses of PFS, OS, and ORR.

**Figure 2 Graphical Approach to Control Familywise Error Rate for Testing Primary and Key Secondary Endpoints**

EP = endpoint; ORR = objective response rate; OS = overall survival; PFS = progression-free survival.  
 Hypothesis ( $H_1$ ): The PFS of lenvatinib + pembrolizumab arm is superior to that of sunitinib arm.  
 Hypothesis ( $H_2$ ): The PFS of lenvatinib + everolimus arm is superior to that of sunitinib arm.  
 Hypothesis ( $H_3$ ): The OS of lenvatinib + pembrolizumab arm is superior to that of sunitinib arm.  
 Hypothesis ( $H_4$ ): The OS of lenvatinib + everolimus is superior to that of sunitinib arm.  
 Hypothesis ( $H_5$ ): The ORR of lenvatinib + pembrolizumab arm is superior to that of sunitinib arm.  
 Hypothesis ( $H_6$ ): The ORR of lenvatinib + everolimus is superior to that of sunitinib arm.

**Table 2 Efficacy Boundaries and Properties for PFS H1 and PFS H2 (LDOF spending function) Based on Initial Assigned Alpha**

Analysis (2 arms)	Value	H 1 ( $\alpha=0.045$ )	H 2 ( $\alpha=0.0049$ ) d
IA: 80% a N: 700 Events: 310 Month: 38	P (2-sided) b	0.0216	0.0014
	HR at boundary c	0.7705	0.6964
	Power	75%	42%
Final: 100% N: 700 Events: 388 Month: 45	P (2-sided) b	0.0386	0.0046
	HR at boundary c	0.8105	0.7491
	Power	90%	69%

HR = hazard ratio, IA = interim analysis, N = number of subjects.

a: Information fraction, percentage of expected number of events at final analysis.

b: *P*-value (2-sided) is the nominal  $\alpha$  for testing.

c: HR at boundary is the approximate HR required to reach an efficacy boundary.

d: The power of H2 test will be at least 90% if H1 and H3 testing are significant.

**Table 3 Efficacy Boundaries and Properties for OS H3 and OS H4 (LD-Pocock Spending function) when PFS Tests Are Significant**

Analysis (2 arms)	Value	H 3 ( $\alpha=0.045$ )	H 4 ( $\alpha=0.0049$ ) d
IA: 45% a N: 700 Events: 137 Month: 38	P (2-sided) b	0.0258	0.0028
	HR at boundary c	0.683	0.600
	Power	44%	20%
IA: 60% a N: 700 Events: 182 Month: 45	P (2-sided) b	0.0152	0.0014
	HR at boundary c	0.698	0.622
	Power	55%	27%
IA: 80% a N: 700 Events: 243 Month: 57	P (2-sided) b	0.0158	0.0014
	HR at boundary c	0.734	0.663
	Power	69%	41%
Final: N: 700 Events: 304 Month: 69	P (2-sided) b	0.0158	0.0014
	HR at boundary c	0.758	0.692
	Power	80%	51%

HR = hazard ratio, IA = interim analysis, N = number of subjects.

a: Information fraction, percentage of expected number of events at final analysis.

b: *P*-value (2-sided) is the nominal  $\alpha$  for testing.

c: HR at boundary is the approximate HR required to reach an efficacy boundary.

d: The power of H4 test will be at least 80% if H1, H3 and H2 are significant.

The nominal  $\alpha$  level for each PFS comparison at the interim and final analyses will be determined by a Lan-DeMets spending function with an O'Brien-Fleming boundary as illustrated in Table 2. The nominal  $\alpha$  level for each OS comparison at the interim and final analyses will be determined by a Lan-DeMets spending function with Pocock boundary as illustrated in Table 3. The actual boundaries will be calculated using the observed number of events at the interim and final analyses and  $\alpha$  passed from previous tests.

### 5.3.4 Examination of Subgroups

For efficacy endpoints, the hazard ratio and two-sided 95% confidence interval (CI) for comparing PFS as assessed by the IIR and investigator assessment of either Arm A versus Arm C or Arm B versus Arm C will be presented in forest plots for the subgroups. Median PFS and 95% CIs will be presented for all subgroups. Similar summary and plots will be provided for OS. In addition, the odds ratio and two-sided 95% CIs for comparing ORR as assessed by IIR will be summarized and presented in forest plots. If sample size of subgroup/strata is less than 18 (5% of sample size in the treatment group), the subgroup/strata may be considered to collapse to the closest subgroup/strata as appropriate.

- Age group (<65 years, ≥65 years)
- Sex (male, female)
- Race (White, Asian, all others)
- Geographic region per IxRS (West Europe and North America, Rest of World)
- MSKCC risk group per IxRS (favorable , intermediate, poor risk)
- IMDC risk group (favorable , intermediate, poor risk)
- Number of metastatic sites per IIR (0, 1, 2, ≥3)
- KPS score group (100-90, 80-70)
- Baseline bone metastasis (yes, no)
- Baseline liver metastasis (yes, no)
- Baseline lung metastasis (yes, no)
- PD-L1 status (CPS≥1, CPS<1, not available)
- Prior nephrectomy (yes, no)
- Histologic clear component featuring sarcomatoid (yes, no)

Additional subgroup analyses may also be conducted, if deemed appropriate.

### 5.3.5 Handling of Missing Data, Dropouts, and Outliers

Adverse Events with incomplete start dates will be considered treatment emergent if:

- a) Day and month are missing and the year is equal to or after the year of the first dose date;
- b) Day is missing, and the year is after the year of the first dose;
- c) Day is missing and the year is equal to the year of the first dose date and the month is equal to or after the month of the first dose date;
- d) Year is missing; or
- e) Complete date is missing.

Medications will be considered concomitant if:

- a) Day and month are missing and the year is equal to or after the year of the first dose date;
- b) Day is missing, and the year is after the year of the first dose;
- c) Day is missing and the year is equal to the year of the first dose date and the month is equal to or after the month of the first dose date; or
- d) Year is missing; or
- e) Complete date is missing.

For incomplete dates involving efficacy and other safety data, a conservative imputation will be used for calculation if needed. More details of imputation rules will be specified in study analysis dataset specification.

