9.5.1.4.1 ADVERSE EVENTS AND EVENTS ASSOCIATED WITH SPECIAL SITUATIONS

An adverse event (AE) is any untoward medical occurrence in a patient or clinical investigation subject administered an investigational product. An AE does not necessarily have a causal relationship with the medicinal product. For this study, the study drugs are lenvatinib, everolimus, pembrolizumab, and sunitinib.

The criteria for identifying AEs in this study are:

- Any unfavorable and unintended sign (including an abnormal laboratory finding), symptom, or disease temporally associated with the use of an investigational product, whether or not considered related to the investigational product (Note: Every sign or symptom should not be listed as a separate AE if the applicable disease [diagnosis] is being reported as an AE.)
- Any new disease or exacerbation of an existing disease. However, worsening of the primary disease should be captured under efficacy assessments as disease progression rather than as an AE.
- Any deterioration in nonprotocol-required measurements of a laboratory value or other clinical test (eg, ECG or x-ray) that results in symptoms, a change in treatment, or discontinuation of study drug
- Recurrence of an intermittent medical condition (eg, headache) not present pretreatment (Baseline)
- An abnormal laboratory test result should be considered an AE if the identified laboratory abnormality leads to any type of intervention, withdrawal of study drug, or withholding of study drug, whether prescribed in the protocol or not

All AEs observed during the study will be reported on the CRF. All AEs, regardless of relationship to study drug or procedure, should be collected beginning from the time the subject signs the study ICF through the last visit. Subjects who fail screening primarily due to AEs must have the AEs leading to screen failure reported on the Screening Disposition CRF. Serious AEs must be collected through 120 days after the subject's last dose of study drug, or for 30 days after the last dose of study drug if the subject initiates new anticancer therapy, whichever is earlier.

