### 5.3.6 Other Considerations

In case subjects who took combination therapy in Arm A and Arm B discontinue one treatment earlier than the other, end of treatment date is defined as the latest date of the last dose dates of two study drugs. All efficacy and safety endpoints will be summarized up to the end of treatment date plus applicable window for each endpoint.

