### 5.6.2 Adverse Events

The AE verbatim descriptions (investigator terms from the CRF) will be classified into standardized medical terminology using the Medical Dictionary for Regulatory Activities (MedDRA). Adverse events will be coded to the MedDRA (Version 21.1 or higher) lower level term (LLT) closest to the verbatim term. The linked MedDRA preferred term (PT) and primary system organ class (SOC) will also be captured in the database. The Common Terminology Criteria for Adverse Events (CTCAE) version 4.03 will be used to assess the severity of AEs.

A treatment-emergent adverse event (TEAE) is defined as an AE that emerged during treatment (up to 30 days after the subject's last dose of study drug), having been absent at pretreatment (Baseline) or

- Reemerged during treatment or up to 30 days following last dose of study drug, having been present at pretreatment (Baseline) but stopped before treatment, or
- Worsened in severity during treatment or up to 30 days following last dose of study drug relative to the pretreatment state, when the AE was continuous.

The serious AE that emerged up to 120 days after the subject's last dose of study drug is also counted as TEAE.

Only those AEs that are treatment emergent will be included in summary tables. All AEs, treatment emergent or otherwise, will be presented in subject data listings.

An overview table, including the incidence of and the number of subjects with TEAEs, TEAEs with grade 3 or above, serious adverse events (SAEs), deaths, and TEAEs that led to treatment discontinuation (discontinuation of both agents in arm A or B), dose reduction, or dose interruption will be provided by treatment arms.

The TEAEs will be summarized by treatment groups. The incidence of TEAEs will be reported as the number (percentage) of subjects with TEAEs by SOC and PT. A subject will be counted only once within a SOC and PT, even if the subject experienced more than 1 TEAE within a specific SOC and PT. The number (percentage) of subjects with TEAEs will also be summarized by maximum severity.

The number (percentage) of subjects with TEAEs will also be summarized by relationship to study drug. Summaries of TEAE incidence rate adjusted by treatment duration will be presented.

In summary, the following TEAE tables will be provided:

- Overview of TEAE and treatment-related TEAE
- TEAE by SOC and PT (Any Grade and Grade  $\geq 3$ , maximum grade 3, 4 and 5)
- TEAE by decreasing frequency of PT

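### SAP 5.3.5 counts an adverse event with an incomplete start date as treatment-emergent even when its recorded end date is before the first dose, against SAP 5.6.2 (minor)

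*SAP*

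**What the plan says.** SAP 5.3.5 opens its rule with "Adverse Events with incomplete start dates will be considered treatment emergent if" and lists five conditions, any one of which is enough:

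- a) only the year is known, and it is the first-dose year or later;
- b) only the day is unknown, and the start year is later than the first-dose year;
- c) only the day is unknown, and the start lies in the first-dose year, worded as "Day is missing and the year is equal to the year of the first dose date and the month is equal to or after" that of first dose;
- d) the year is missing;
- e) the whole date is missing.

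No condition refers to the end date of the event.

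SAP 5.6.2 defines a TEAE as "an AE that emerged during treatment (up to 30 days after the subject's last dose of study drug"), absent at pretreatment, or else as an event that came back or worsened in that period. For serious events it adds: "The serious AE that emerged up to 120 days after the subject's last dose of study drug is also counted as TEAE". Only TEAEs go into the summary tables; every AE is listed.

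Protocol 9.5.1.4.1 says that AEs "should be collected beginning from the time the subject signs the study ICF", and the Pre-randomization Phase may last up to 28 days (Protocol 9.1.1). The database will therefore hold events that began, and some that ended, before treatment.

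SAP 5.3.6 adds: "All efficacy and safety endpoints will be summarized up to the end of treatment date plus applicable window for each endpoint".

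**The concern.** A partial-date convention should settle cases that the data leave open. Where an end date is recorded and falls before the first dose, nothing is open: whatever the missing day or month was, the event was over before treatment began. SAP 5.3.5 still labels it treatment-emergent, while SAP 5.6.2 excludes it.

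At stake is the accuracy of the safety tables. Events known to be pre-treatment would be counted in TEAE incidence, worst-grade and exposure-adjusted summaries. If such an event fell in a clinically significant or special-interest category, SAP 5.6.2.2 would also require its time from first dose to onset, and every onset date compatible with the record gives a negative value.

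**Working it through.** The plan gives no figure to reproduce, so this is a check of two rules against each other.

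**Notation.** F = first dose, L = last dose, S = true start of the event, E = recorded end, w = 30 days (120 if serious). SAP 5.6.2 can be met only if some S compatible with the record satisfies F ≤ S ≤ L + w. Since S ≤ E, a record with E < F has S < F for every possible completion of its start date, so it cannot be a TEAE.

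**Which rules let such a record through?**

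- Rule a): yes, when the known year is the first-dose year.
- Rule b): no. The start year is after the first-dose year, so S > F and a valid E cannot precede F.
- Rule c): yes, when the known month is the first-dose month. In later months S > F.
- Rules d) and e): yes, because they apply whatever the end date is.

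The conflict therefore lies in a), c), d) and e).

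**Worked cases** (illustrative dates: F = 20 Mar 2018, L = 10 Jan 2019). Twenty-eight days before F is 20 Feb 2018, and 1 to 19 March are pre-dose days inside the first-dose month. L + 30 days = 9 Feb 2019; L + 120 days = 10 May 2019.

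| Case | Known start | Known end | SAP 5.3.5 list | Possible under SAP 5.6.2? |
|---|---|---|---|---|
| 1 | Mar 2018 | 12 Mar 2018 | TEAE, rule c) | No |
| 2 | 2018 | 25 Feb 2018 | TEAE, rule a) | No |
| 3 | none | 12 Mar 2018 | TEAE, rule e) | No |
| 4 | Mar 2018 | unknown | TEAE, rule c) | Yes |
| 5 | Feb 2019 | unknown | TEAE, rule b) | Yes |
| 6 | Mar 2019 | unknown | TEAE, rule b) | No if non-serious; yes if serious |
| 7 | Jun 2019 | unknown | TEAE, rule b) | No |

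Cases 1 to 3 are the defect: nothing elsewhere in the two documents removes them. In cases 4 and 5 the rule is a reasonable conservative default that agrees with SAP 5.6.2. Cases 6 and 7 conflict only if the list in 5.3.5 is read alone; SAP 5.3.6 cuts safety summaries off at end of treatment plus the applicable window.

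**After the fix.** With an exception for E < F, cases 1 to 3 become not treatment-emergent. Cases 4 to 7 are classified as before, with 6 and 7 still subject to SAP 5.3.6.

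**Size.** The documents give no count of incomplete dates or of screening-period events. As an illustration on assumed values only: if 1% to 3% of AE records lack a start day, 2% to 5% of AEs arise before the first dose, and the two are independent, then 0.01 × 0.02 = 0.02% to 0.03 × 0.05 = 0.15% of records have both features. Under rule c), misclassification also needs a recorded end before the first dose and a start in the first-dose month, so fewer would be affected. Records with less of the date known are not covered by this product.

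**The case against.** The strongest reply is that 5.3.5 is a missing-data convention and 5.6.2 is the definition. Read together, the convention fills in only what the definition cannot decide, and counting a doubtful event as treatment-emergent is the cautious direction for safety. This is right for records whose end date is unknown or on or after the first dose. It does not rescue the others, because 5.3.5 states its rule without that limit. SAP 5.2.5 shows how the limit could be written: its default for medications covers only those whose status cannot be determined from the dates.

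A second reply is that an end-date check may sit in the programming and dataset specifications, which SAP 5.3.5 and Section 9 place in separate documents. That is possible and cannot be checked here. However, the deferral in 5.3.5 follows a sentence on efficacy and other safety data, whereas the AE rule is given as a finished list. A specification with the check would depart from the SAP as written.

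A reader might also infer two larger faults that the documents do not support:

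- **That the 30-day limit is lost for incomplete dates.** It is missing from the 5.3.5 list, but SAP 5.3.6 applies the relevant window to all safety endpoints and 5.6.2 gives the windows. Protocol 9.1.2.1 ends general AE capture at 30 days and SAE collection at 120 days after the last dose, or at 30 days if new anticancer therapy starts. Protocol 9.5.4.1 allows later reports of related serious events, but the SAP 5.3.6 cut-off still applies to them.
- **That the parallel medication list has the same fault.** SAP 5.2.5 requires a medication started before the first dose to be continuing at that dose. A medication known to have stopped earlier is therefore determinable as prior.

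**Conclusion.** Wrong as written, but minor. Rules a), c), d) and e) of SAP 5.3.5 class as treatment-emergent some events whose recorded end date shows that they were over before treatment, contrary to SAP 5.6.2. It would go too far to say that 5.3.5 contradicts the TEAE definition for every incomplete start date in or after the first-dose month: where timing is truly unknown, the two sections agree.

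The error runs one way, adding TEAEs. Its size cannot be derived from the documents; the percentages in the working are assumptions, and the true effect is likely very small. The rule is the same in every arm, the safety summaries are descriptive, and the PFS, OS and ORR tests do not depend on it. The conclusion rests on the SAP text as it stands and on at least some screening-period events having a complete end date but an incomplete start date.

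**What to change.** Add one clause to SAP 5.3.5: rules a) to e) apply unless the known end date of the event is before the first dose of study drug. Events excluded in this way remain in the AE listings, so no information is lost.

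Optionally, for clarity only, add cross-references in 5.3.5 to 5.3.6 and 5.6.2 for the 30-day and 120-day windows, and to 5.2.5 for medications.

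The cost is one sentence in the SAP and a few lines of programming. No change to data collection, sample size or efficacy analysis is needed.
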